### **Coronary Artery Bypass Grafting (CABG)**

A type of surgery that improves blood flow to the heart. During CABG, a healthy artery or vein from the body is connected, or grafted, to the blocked coronary artery. The grafted artery or vein bypasses (that is, goes around) the blocked portion of the coronary artery. This creates a new path for oxygen- rich blood to flow to the heart muscle. Surgeons can bypass multiple coronary arteries during one surgery.

### **Percutaneous Coronary Intervention (PCI)**

Also called coronary angioplasty, this is a procedure used to open clogged heart arteries. Angioplasty involves temporarily inserting and inflating a tiny balloon where the artery is clogged to help widen the artery.

### **Ventricular Fibrillation**

A condition in which there is uncoordinated contraction of the cardiac muscle of the ventricles in the heart, making them quiver rather than contract properly.

### **Ventricular Tachycardia**

A type of tachycardia, or a rapid heartbeat, that starts in the bottom chambers of the heart, called the ventricles.

### **Other cardiac surgeries**

Any other surgery on the heart (excluding CABG). Examples include ventricular assist device, pacemaker, valve repair, and heart transplant.

## **13. QUALITY CONTROL ACTIVITIES**

### **13.1 Training Sessions and Certification Procedures**

An Operations Manual details overall study processes and procedures. It will contain instructions describing how the study is conducted, what procedures are performed, in what order, by whom, and under what circumstances. Investigator and study coordinator training sessions will be held to provide appropriate instruction regarding the study.

### **13.1.1 Genotyping via SPARTAN® Bioscience**

Spartan Bioscience will provide installation and training of personnel to use the equipment and run the buccal swabs. Each study site will receive a Spartan Analyzer. Spartan will perform instrument installation. Following equipment installation, Spartan will provide training to study personnel at each site. Each trainee will have the opportunity to run a minimum of two independent runs with the Spartan *CYP2C19* assay, and Spartan will additionally guide the trainees through more runs as needed to ensure independent trainee competency in performing the assay from start to finish.

Each site will perform analytical validation of the Spartan platform's performance characteristics prior to analyzing study samples. Buccal swabs obtained from volunteers will be analyzed on the Spartan instruments and compared to oral fluid DNA results obtained from a currently existing validated *CYP2C19* automated fluorescent Sanger sequencing assay. All non-Rochester sites will obtain buccal swabs for analysis on their own Spartan instruments and ship one oral fluid sample to Mayo Rochester for *CYP2C19* sequence analysis.

### **13.1.2 Genotyping via ABI TaqMan**

The laboratory performing this assay has extensive experience with this platform. Probes and primers will be designed utilizing ABI's design services. Development and analytical validation will occur as per the laboratory's established guidelines. The laboratory will utilize a currently existing validated *CYP2C19* automated fluorescent Sanger sequencing assay to verify accuracy of the TaqMan assay as well as troubleshoot any potential samples with unclear genotypes via the TaqMan assay. Each operator of the assay will be trained as per the laboratory guidelines.

### **13.1.3 Database Training**

AHRC, DCIS, and the Project Coordinator will arrange for each individual site coordinator to be trained with the variable definitions and data sources to ensure uniform data collection across study sites.

## **14. PARTICIPANT SAFETY, ADVERSE EVENTS, CLINICAL ENDPOINTS, AND OTHER REPORTING**

### **14.1 Institutional Review Boards**

Before initiating this study, the protocol, informed consent forms, recruitment materials, and other relevant information will be reviewed and approved by Mayo Clinic and respective institutional review boards (IRB) or research ethics boards (REB). Any amendments to the protocol must be approved by each institution's IRB or REB before they are implemented. Any amendments to the protocol and consent form(s) will be communicated to the sites upon Mayo IRB approval.

### **14.2 Adverse Events**

All subjects randomized to conventional therapy will receive clopidogrel; subjects randomized to the prospective genotyping group will receive clopidogrel or ticagrelor based on their genotype. Known adverse events associated with both medications will not be considered study related and will not be recorded as such in the trial because they have already been identified with the specific antithrombotic therapy, which is clinically indicated for the subjects' clinical

care. However, participating sites must follow the policy of the IRB/REB they are utilizing, which may include reporting of these events to their respective ethics board.

Adverse event reporting and monitoring is applicable to the study-specific procedures of this study, including a blood draw, three buccal swabs (in the prospective genotype arm), a genotyping survey (first 1,000 subjects) randomization, and genotype analysis (which will be used in the prospective genotype arm to determine which of two FDA-approved antithrombotic treatments will be used as prophylactic therapy for PCI). Any adverse event related to study-specific procedures must be reported to the Project Coordinator.

In addition, any problem or event which, in the opinion of the local investigator, was unanticipated, places subjects or others at a greater risk of harm than was previously known or recognized, and was possibly related to the research procedures will be reported to the Project Coordinator within 48 hours of notification. The site coordinator will record the information in the source documentation and will forward all relevant medical information to the Project Coordinator who will prepare the documents for Adjudication Committee review.

### **14.3 Clinical Endpoints**

Information on all clinical endpoints will be recorded in the source documentation and in the eCRF. This information will be adjudicated by an independent Adjudication Committee that will be blinded to study treatment.

When a MACE is suspected, the site coordinator and/or PI will notify the Project Coordinator. The site coordinator will record the information in the source documentation and in the eCRF and will forward all relevant medical information to the Project Coordinator who will prepare the documents for Adjudication Committee review.

When any bleed requiring diagnostic study or intervention (e.g. doctor's visit, change in medication, ER visit, hospitalization) is suspected, the site coordinator will record the information in the source documentation and in the eCRF and will forward all relevant medical information to the Project Coordinator who will prepare the documents for Adjudication Committee review.

### **14.4 Other**

Known adverse events associated with both medications will not be considered study related and will not be recorded as such in the trial because they have already been identified with the specific antithrombotic therapy, which is clinically indicated for the subjects' clinical care. However, when any death occurs, the site coordinator will record the information in the source documentation and in the eCRF and will forward all relevant medical information to the Project Coordinator who will prepare the documents for Adjudication Committee review.

## **15. STATISTICAL CONSIDERATIONS**

### **15.1 Study Design**

This is a multicenter, prospective, two-arm, unblinded trial with 1:1 randomization between the conventional therapy arm treated with clopidogrel at standard dose and a prospective genotype tailored approach using clopidogrel in WT and ticagrelor in reduced function *CYP2C19* genotype subjects. Subjects in the conventional therapy group will undergo retrospective genotyping one year after PCI to identify those with reduced function *CYP2C19* alleles. The study goal is to assess the effectiveness of ticagrelor in reducing the risk of 1-year MACE in

subjects who carry the reduced function *CYP2C19* allele. Subjects will be followed by telephone contact for 1 year after index PCI. Endpoint analysis will occur after all subjects have reached the study endpoint. Predefined major protocol violations/deviations are missing data for the primary efficacy end point, violation of inclusion criteria, and additional protocol violations that will be possibly defined during the blind data review. Missing patients will be censored at the last follow-up visit. Alive or dead status will be specifically searched for all missing patients.

## 15.2 Sample Size and Power Considerations

### 15.2.1 Primary Endpoint

Sample size and power calculations for the study are based on the following assumptions:

- 2-sided log-rank test
- $\alpha = .05$
- Randomization ratio of 1:1

Data from the Mayo Rochester PCI registry demonstrate a 1 year rate of death, MI, or stroke of about 7.5% in PCIs from 2008-2009. Furthermore, the PLATO trial suggests we can expect stent thrombosis or severe, recurrent ischemia in about an additional 3%, resulting in a baseline rate of 10.5%. The rate is expected to be higher in \*2 or \*3 allele carriers who are discharged on clopidogrel, thus we assume a baseline rate of 12% for primary endpoint in the control arm.

Two studies suggest that the expected rate of 12% in Korean patients treated with clopidogrel after PCI for ACS. Kim et al. observed a 10.1% event rate for death, myocardial infarction, or stroke at 12 months in 306 patients with at least one *CYP2C19*\*2 or \*3 allele treated with PCI for acute myocardial infarction. As noted above, the PLATO trial suggests that stent thrombosis and severe recurrent ischemia may add 3% to this rate, which would result in a baseline rate over 12%. Oh et al. observed a 10.7% event rate for cardiac death, myocardial infarction and repeat revascularization at 12 months in 1011 patients treated with a drug-eluting stent (22% AMI, 78% stable) and carrying at least one *CYP2C19*\*2 allele. Assuming the event rate is higher in the

AMI subgroup and that the addition of stent thrombosis to the endpoint would increase the event rate, this study also suggests that a 12% event rate in the control group of Koreans may be expected.

Given that the vast majority of patients at the Mayo sites are of European heritage, we expect a reduced function allele prevalence of about 30% in those patients. The Canadian hospitals have a more diverse ethnic mix of patients, and we expect their prevalence to be anywhere from 30-50%. Thus, our sample size calculations assume an overall prevalence of reduced function allele carriers of 30% among patients recruited at those sites. We also assume the prevalence to be 50% in patients enrolled from South Korea and expect to enroll 1,015 subjects from there. Furthermore, we assume no more than 5% of patients will be lost to follow-up or drop out.

Based on data from Mega and Schuldiner, a hazard ratio as low as 0.60 for ticagrelor versus clopidogrel in reduced function allele carriers may be expected. We intend to power the study to detect a hazard ratio of 0.65 or smaller. This will

require a total of 1,694 patients with reduction function alleles to be randomized, and thus 5,270 patients will be enrolled.

**Table 3.** Required sample size for 80% power

	Minimum detectable effect, hazard ratio		
	0.60	0.65	0.70
Number with reduction function allele required	1,241	1,694	2,401
Number with reduced function to enroll assuming 5% drop out	1,307	1,784	2,528
Number with reduced function allele enrolled at South Korean sites	508	508	508
Number with reduced function allele to enroll at non-Korean sites	799	1,276	2,020
Total number enrolled at Korean sites, assuming 50% prevalence	1,015	1,015	1,015
Total number to enroll at non-Korean sites, assuming 30% prevalence	2,665	4,255	6,734
Total number enrolled	3,680	5,270	7,749

### 15.2.2 Revised Sample Size Calculations

At the time of this protocol revision (Version 8), the estimated event rate for the primary endpoint across all LOF subjects is 4.8%, substantially lower than the assumptions made in Section 15.2.1. We propose performing updated power calculations using a revised minimum detectable effect of a hazard ratio of 0.50. This effect size is justified by several arguments. First, ticagrelor has already been shown to reduce MACE events by about 16% in all ACS patients, regardless of genotype, in the PLATO trial. However, because our study treatment represents a precision medicine, pharmacogenomic approach, we expect a much greater treatment effect in the targeted LOF population. Second, such effect sizes have been seen in other studies involving CYP2C19 \*2 and \*3 alleles(2,40). Third, a meta-regression analysis of studies comparing event rates in (primarily) clopidogrel-treated patients who were LOF vs. WT suggested an inverse relationship between the overall event rate and the WT vs. LOF advantage, such that the predicted HR

in very low event rates was consistent with 0.50. Finally, at low event rates, a large effect must exist within the LOF population in order to achieve reasonable number-needed-to- treat (NNT) values, since the genotype-guided dual antiplatelet treatment is expected to have no effect in the WT population. For example, if the event rate is 4% in LOF subjects on clopidogrel, and 2% in LOF subjects on ticagrelor, that 50% reduction would equate to a NNT of 50 subjects within the LOF sub-population. If the prevalence of LOF alleles is 30% in the overall population, that would equate to an NNT of 167. Under initial assumptions, the NNT in the LOF sub-population would have been 25 subjects, equating to an overall NNT of 75. Thus, from the perspective of NNT, we are powered to detect a smaller effect than under initial assumptions.

Additional assumptions play a role in the power calculations. First, we assume that around the total enrollment mark of 3900 subjects, 20% of subjects enrolled from

that point forward will be from Korea. This is lower than observed so far (30%), due to the impending activation of additional sites in North America. Increasing this percentage would result in a smaller required sample size, as it would increase the prevalence of LOF subjects in the study. We also assume that the current prevalence of LOF carriers will continue in Korean (59%) and North American (28%) subjects. Increasing either of these prevalences would reduce the number of subjects required. The power calculations are based on a two-sided log-rank test at a Type I error rate of 0.05 with an expected randomization ratio of 1:1. Table 3 demonstrates the calculations for total subjects enrolled assuming an event rate of 4.5%. Table 4 gives required sample sizes for varying event rates and power levels. These tables show that the previous planned sample size of 5270 subjects provides at least 80% power if the event rate is at least 4.0%.

**Table 4.** Revised Sample Sizes for a Minimum Detectable Hazard Ratio of 0.50 with an overall event rate of 4.5%

	80% Power	85% Power	90% Power
N of LOF subjects required	1560	1784	2086
N of LOF subjects accounting for 5% dropout	1643	1878	2196
N of LOF patients expected from Korea	747	828	937
N of LOF patients expected from North America	896	1050	1259
Total patients expected from Korea	1275	1413	1599
Total patients expected from North America	3192	3742	4486
Total number of patients to enroll	4467	5155	6085

**Table 5.** Required Sample Sizes for a Minimum Detectable Hazard Ratio of 0.50 at varying event rates and power assumptions

Baseline event rate	Power at n=5270	Sample size needed for given power		
		80%	85%	90%
5.0%	89.3%	3955	4570	5409
4.5%	85.8%	4467	5155	6085
4.0%	81.6%	5052	5827	6875

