## 15.8 Monitoring for Futility and Efficacy

Both efficacy and futility monitoring require three estimates: 1) a best current estimate of the treatment effect, as well as 2) uncertainty of the estimate (standard error and/or confidence interval), and 3) an estimate of what proportion of the study's final information is currently in hand, that is, the current value of "information time".

Information time is critical both in assessing conditional power (futility) as well as in doing interim testing using group sequential approaches. Appendix C details how to

construct a combined likelihood combining the information from the complete and the incomplete subject data, which produces the first two required estimates, using likelihood calculations, and specifically, using the profile likelihood method to get down to the one-dimensional likelihood for the treatment effect parameter.

Appendix C also details how to estimate information time (the third required measure). Once we have a current z-score (effect divided by standard error) for the treatment effect, as well as our current estimate of information time, we can then do standard calculations for conditional power (futility) and efficacy

**Futility Monitoring:** We propose that this assessment be based on our calculation of conditional power, as described in Appendix C. In addition to the conditional power calculation, we will provide the modified unconditional power calculation based on current estimates of event rates and the estimate and 95% CI of the average event rate in LOF subjects. We specifically propose that at the time of DSMB reviews, that consideration be given to stopping the trial if the ratio of conditional power to initial power falls below the proportion of remaining information time. For example, if the initial power is 85%, and the proportion of remaining information time is 40%, then the conditional power should exceed 34% ( $0.85 \times 0.4$ ). The basis for the moving target of conditional power is the “sunk cost” argument. The initial study design is assumed to equate the expected utility of a positive result with the cost of the entire study. By equating the ratio between conditional power and initial power, the cost-benefit ratio is maintained. This means that the bar for conditional power for continuing gets progressively lower, as more of the total study costs become a “sunk cost.”

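### Does Table 5's baseline event rate overstate the power that 5,270 subjects provide?

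*Combined protocol and SAP*

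**What the plan says.** Section 15.2.1 sets the original design: "we assume a baseline rate of 12% for primary endpoint in the control arm". Table 3 gives the carriers required for 80% power at hazard ratios of 0.60, 0.65 and 0.70.

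Section 15.2.2 revises the calculation because "the estimated event rate for the primary endpoint across all LOF subjects is 4.8" per cent. The target hazard ratio becomes 0.50. Table 4's title specifies a "Minimum Detectable Hazard Ratio of 0.50 with an overall event rate of 4.5" per cent. Table 5 then lists rates of 5.0, 4.5 and 4.0% under the header "Baseline event rate", with power at 5,270 of 89.3, 85.8 and 81.6%. The text concludes that the planned size "provides at least 80% power if the event rate is at least 4.0" per cent, without naming an arm.

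The same section supports the larger effect with a number-needed-to-treat (NNT) example: "if the event rate is 4% in LOF subjects on clopidogrel, and 2% in LOF subjects on ticagrelor". It concludes that "from the perspective of NNT, we are powered to detect a smaller effect than under initial assumptions".

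**The concern.** Taken in order, the two sections invite a misreading. Baseline is attached to the control arm in 15.2.1, reappears as the header of Table 5, and between the two the NNT example uses 4% as a clopidogrel-arm rate. A reader who carries that 4% to Table 5 finds 81.6% power.

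If the rates were clopidogrel-arm rates, a hazard ratio of 0.50 would leave roughly three quarters as many events as a pooled rate of the same size. Every power in Table 5 would then be about 7 to 12 points too high, and the 80% floor would fail at 4.0%. That floor is the section's stated reason for keeping 5,270. The NNT example also has a pooled rate of 3%, below every row of Table 5, although it precedes a statement about what the trial is powered to detect.

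**Working it through.** **Inputs.** Two-sided alpha 0.05, 1:1 allocation, hazard ratio (HR) 0.50, 5% dropout (15.2.2). Rates, LOF numbers and totals come from Tables 3 to 5. The ticagrelor-arm rate is pT = 1 − (1 − pC)^HR, where pC is the clopidogrel-arm rate.

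**1. Table 3 uses the control-arm rate.** Events by Schoenfeld's formula are d = 4(1.960 + 0.842)² / (ln HR)². At HR 0.65, d = 169.2. With pC = 12%, pT = 7.97% and the mean is 9.99%, so N = 169.2 / 0.0999 = 1,694. The three hazard ratios give 1,241, 1,694 and 2,401, exactly as printed. Treating 12% as a pooled rate gives 1,003, 1,410 and 2,057.

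**2. Table 4 uses the pooled rate.** A mean of 4.5% at HR 0.50 gives pC = 5.97% and pT = 3.03%. The two-proportion formula, with p̄ the mean rate, is

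N = 2 × {1.960 √[2p̄(1 − p̄)] + z √[pC(1 − pC) + pT(1 − pT)]}² / (pC − pT)²

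At 80% power (z = 0.842) this is 2 × (0.5746 + 0.2461)² / 0.02939² = 1,560.

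| Power | Stated LOF N | 4.5% pooled | 4.5% on clopidogrel |
|---|---|---|---|
| 80% | 1,560 | 1,560 | 2,075 |
| 85% | 1,784 | 1,784 | 2,373 |
| 90% | 2,086 | 2,087 | 2,777 |

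**3. LOF subjects at 5,270.** Table 4 at 85% power has 1,413 Korean subjects in 5,155. Adding 20% of the remaining 115 gives 1,436, which leaves 3,834 from North America. Table 4's prevalences are 747/1,275 = 58.6% and 896/3,192 = 28.1%. LOF enrolled: 1,436 × 0.586 + 3,834 × 0.2806 = 1,917. Evaluable: 1,917 × 0.95 = 1,821.

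**4. Table 5 on both readings, 1,821 evaluable, HR 0.50.** In the last column the first figure is from the two-proportion formula that reproduces Table 4, the second from Schoenfeld's formula.

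| Rate | Stated power | Rate pooled (implied pC vs pT) | Rate on clopidogrel |
|---|---|---|---|
| 5.0% | 89.3% | 89.1% (6.6 vs 3.4%) | 79 to 82% |
| 4.5% | 85.8% | 85.7% (6.0 vs 3.0%) | 75 to 78% |
| 4.0% | 81.6% | 81.4% (5.3 vs 2.7%) | 70 to 73% |

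Total enrolment for 80% power at 4.0% is about 5,070 on the pooled reading (5,052 stated) and about 6,860 if 4.0% is the clopidogrel-arm rate. Table 5's stated totals at 5.0% and 4.0% are matched to within about 1%, not exactly.

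**5. The observed rate.** A pooled 4.8% at HR 0.50 is 6.4% versus 3.2%, with about 88% power.

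**6. The NNT example.** 4% versus 2% has a mean of 3% and about 71 to 74% power. The conclusion does not depend on it. At Table 5's lowest row, NNT = 1 / (0.0531 − 0.0269) = about 38. Under the initial design it was 1 / (0.12 − 0.0797) = about 25. The larger NNT is the smaller absolute effect, so the statement holds at a rate where power exceeds 80%.

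**The case for a change.** The best case for an edit is that the floor sentence carries the decision to stay at 5,270, and a plan should not need back-calculation to show which rate its floor refers to. Both rates are in use: Sections 15.9.1 and 15.9.2 estimate the conventional-arm LOF rate, while 15.8 reports "the estimate and 95% CI of the average event rate in LOF subjects". Appendix G lets the DSMB advise a larger sample if the endpoint rate is low. A member who compared a conventional-arm 4.0% with Table 5 would believe power was about 82% when it was about 70 to 73%.

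What stands is that the header is a poor label and the floor sentence could name its rate. The rest is weaker. The meaning can be recovered without calculation: the section starts from a rate across all LOF subjects, Table 4 says overall, and Table 5's 4.5% row repeats Table 4's totals of 4,467, 5,155 and 6,085, so both tables use one rate. Nor is baseline reserved for the control arm in 15.2.1, which also applies it to a 10.5% figure built from a PCI registry before any allowance for carrier status. No rule makes the mistaken lookup: 15.9.1 and 15.9.2 compute power from a prior and the observed data without citing Table 5, and 15.8 sets its updated power beside the average LOF rate, which is the matching quantity. The 4% versus 2% figures are an illustration, not a design row.

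**Conclusion.** The concern identifies a real labelling slip but no error in the design. Read as the rate over both LOF arms, Table 4 reproduces to within one subject and the powers in Table 5 to within 0.2 percentage points. The floor is true as intended: a pooled 4.0% at HR 0.50 means about 5.3% on clopidogrel and gives about 81% power. The 85.8% used in Appendix C, the sample size, the monitoring rules and the direction of the NNT conclusion all stand. The 10-point gap arises only for a reader who overrides the section's own cues, and no decision in the plan requires that. The text's citing of Tables 3 and 4 for what are Tables 4 and 5 is a clerical slip of the same kind.

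This rests on the LOF count at 5,270 being interpolated from Table 4, and on HR 0.50. The 5.3% equivalent is specific to that hazard ratio: a pooled 4.0% would mean about 5.0% on clopidogrel at HR 0.60. The clopidogrel-arm figures are ranges because the two-proportion and Schoenfeld formulas differ by about 3 points at these rates. No change to the plan follows.
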